--	--

	
the study which may be modified for symptomatic treatment during the study in accordance with usual practice.
 
Treatment Visit/Observational Visit 1 (TV/OV1): At least 7 days after SV2
 
Patients will complete the Screening ON/OFF Episodes Log and PD Diary for the 3 consecutive days prior to TV/OV1.
 
Patients will report to the clinic after having taken their usual PD medications prior to the visit. The timing of arrival for TV/OV1 should be scheduled to increase the likelihood that patients will be in the ON state upon arrival (i.e., they should arrive to the clinic as shortly as feasible after taking their standard oral PD medications at home). Patients will bring to the clinic all of their usual PD medications.
 
The clinic staff will collect the Screening ON/OFF Episodes Log and PD Diary, review the information, sign and date each, and confirm that the DLco assessment was performed prior to the visit (and if not, the study visit must be re-scheduled).
 
Clinic staff will record the time patients took their usual PD medications prior to the visit and record any changes in standard PD medication dose/regimen. The following assessments will be performed: review of concomitant medications; PDQ-39 (in an ON state); brief physical examination; UPDRS Part 2 (preferably in the ON state); S&E ADL scale (preferably in the ON state); ECG; standard and orthostatic BP and HR; RR; spirometry (preferably in the ON state); clinical laboratory tests (with documentation of fasting status) including serum pregnancy test, if applicable; C-SSRS; Epworth Sleepiness Scale; and the QUIP.
 
In addition for the CVT-301 treated group only:
 
Clinic staff will distribute the Inhaled Dosing Log for recording the number of times the inhaler was used and the number of capsules used for each inhalation (to be completed daily throughout the 12-month treatment period).
 
Clinic staff will distribute the PD Diary which will be used to record time OFF, time ON without dyskinesia, time ON with non-troublesome dyskinesia, time ON with troublesome dyskinesia, and time asleep (to be completed for the 3 consecutive days prior to the treatment visits). The UPDRS Part 4 (Questions 32-35 and 36-39) will be completed.
 
The clinic staff will provide study drug kits.
 
Patients will be trained again on the proper technique to prepare and use the inhaler system (using sham capsules) per the IFU.
 
Under clinic staff supervision, preferably between 2 and 5 hours after receiving their previous dose of oral PD medications (in the OFF state), patients will prepare and self-administer their entire dose of inhaled study drug. The dosing time is defined to be when the patient's OFF state is recognized by both the patient and investigator to be at a level similar to the investigator-confirmed severity experienced at SV1 and preferably between 2 and 5 hours after their

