--	---

	
prior oral PD medication.
 
Vital signs (standard vital signs [BP and HR] and orthostatic vital signs [BP and HR]) will be assessed at 20 and 60 minutes post-dose. Respiratory rate will be assessed at 10, 20, 30, and 60 minutes post-dose. Patients will be monitored for AEs throughout the visit. Upon completion of the 60-minute observations, the patient's usual schedule of standard PD medications will be resumed for the remainder of the day (the patient may use the inhaled study drug up to 4 more times at home that day after he/she leaves the clinic, if needed for OFF episodes).
 
Clinic staff will arrange to speak with patients by telephone 1 to 3 days after the visit to monitor for AEs and to discuss concerns or challenges with the inhaler systems or Inhaled Dosing Log.
 
All Patients:
 
The next study visit will be scheduled.
 
Clinic staff will arrange to speak with patients by telephone 2 weeks before TV/OV2 to address any concerns or challenges with the inhaler systems, PD Diary, or Inhaled Dosing Log (CVT arm only), to monitor for any AEs, to confirm the next study visit, to ask the patients how many empty study drug kits will be returned at the next visit (CVT arm only), and also to remind patients of the study procedures required prior to the next scheduled study visit (including completion of the PD Diary and applicable, the Inhaled Dosing Log).
 
At-Home Dosing for the CVT-301 Treatment Group
 
At TV/OV1, TV/OV2, TV/OV3, TV/OV4, and TV/OV5, patients in the CVT-301 treatment group will receive study drug kits and the IFU to take home with them. Patients will be instructed to take their standard oral PD medications as prescribed on their usual schedule of administration, which may be modified as needed for symptomatic treatment during the 12-month study. Additions to and/or modification of the patient's usual PD treatment regimen may take place. Oral PRN LD formulations are not permitted for these patients (refer to Section 9.4.2 of the protocol for a list of prohibited treatments and prohibited medications). The total daily LD dose of the modified PD treatment regimen (not including CVT-301) must not exceed 1600 mg per day.
 
Patients will be instructed to administer inhaled study drug up to 5 times during the waking day as close as possible to the time when they begin to experience OFF symptoms. The PD symptomatology defining the onset of an OFF state may vary by patient, but typically is indicated by the return of PD motor symptoms such as tremor or bradykinesia; for some patients, OFF episodes may be heralded by non-motor symptoms (e.g., pain or anxiety) shortly prior to the appearance of motor symptoms.
 
Study drug may not be used for the treatment of early morning OFF periods (i.e., morning akinesia). Patients may not take their inhaled study drug within 45 minutes following their previous dose of standard oral PD medication. These patients may not take oral PRN

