	
(TEAEs) will be summarized by body system and preferred term. For patients in the observational cohort, the AEs collected between TV/OV1 and TV/OV6 (or Early Withdrawal Visit) will be considered as TEAEs. Furthermore, the time of onset of the TEAEs will be summarized. For vital signs, ECG parameters, spirometry measurements, and DLco, the changes from pre-dose to post-dose assessments of the corresponding day will be calculated and described using descriptive statistics. For spirometry, DLco, and safety laboratory variables, the differences in pre-dose values between the study days will be described. Furthermore, the changes in the spirometry values and difference between the groups will be estimated using a Mixed Model for Repeated Measurements (MMRM) similar to the one used for the exploratory endpoint variables. The proportion of patients with abnormal spirometry values will be tabulated using different criteria for the threshold (e.g., at least 10% or 20% change from baseline at any single visit, at least 10% or 20% change from baseline on at least 2 consecutive visits). The proportions of patients meeting ATS quality criteria (and also for those 'rejected') will be summarized. All spirometry analyses will be performed both for all patients regardless of the ATS quality criteria and separately excluding the assessments not meeting the ATS quality criteria. Changes from baseline to follow-up in the rating scales for assessing suicidality, somnolence, and impulse control disorders will be summarized descriptively. Demographics and baseline characteristics will be summarized descriptively.
 
Exploratory Endpoint Analyses
 
The objectives related to the exploratory endpoints will primarily be assessed for the CVT-301-treated patients. The same objectives will be explored for the pool of CVT-301 naïve patients and patients who were previously enrolled in the CVT-301-002 or CVT-301-003 studies, if feasible.
 
The changes from baseline in continuous exploratory endpoint variables will be estimated using an MMRM. The model will include visit and the stratification variables (Hoehn and Yahr stage and screening FEV1 and/or FEV1/FVC) as fixed factors. The baseline value will be used as a covariate.
 
The categorical data will be primarily evaluated descriptively. Each visit will be evaluated separately for the categorical endpoints.
 
The exploratory endpoint data collected from the patients in the observational cohort will be summarized with descriptive statistics.

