10.3.1. Telephone Calls Before Treatment/Observational Visits

- Telephone calls should be made to patients 4 to 6 days before TV/OV1 for the following reasons: to confirm the DLco assessment has been done (must be completed prior to TV/OV1); to confirm the next study visit; to remind patients to complete the PD Diary and the Screening ON/OFF Episodes Log for the 3 consecutive days prior to the visit; to remind them to bring the PD Diary, Screening ON/OFF Episodes Log, and all of their PD medications with them to the visit; to remind them to take their usual morning medications and eat their standard breakfast prior to the visit; and to remind them to note the time when they take these morning medications. In addition, the site should remind patients that they must be symptom-free of any flu-like syndrome or other respiratory infection for at least 3 days prior to the visit and that they should contact the site if an intervening illness occurs prior to TV/OV1. If a patient has any of these symptoms within this time period, reschedule this visit after these symptoms have been resolved for at least 3 days. The screening period may be extended for up to 2 weeks to accommodate this recovery.
- Telephone calls should be made to patients in the CVT-301 treatment arm 1 to 3 days after TV1 to address any potential concerns or challenges with the inhaler systems or Inhaled Dosing Log.
- Telephone calls should be made to patients in the CVT-301 treatment group 2 weeks (\pm 3 days) before TV2, TV3, TV4, and TV5, and TV6 for the following reasons: to address any concerns or challenges with the inhaler systems, PD Diary, or Inhaled Dosing Log; to monitor for any AEs; to confirm the DLco assessment has been done/scheduled (prior to TV3, TV4, TV5, and TV6); to confirm the next study visit; to remind patients to complete the PD Diaries for the 3 consecutive days prior to TV2, TV3, TV4, TV5, and TV6; to remind patients to complete the Inhaled Dosing Log every day during the treatment period; to remind them to bring their PD Diaries, Inhaled Dosing Logs, study drug kits, and all of their PD medications with them to the visits; to remind them to take their usual morning medications and eat their standard breakfast prior to the visits; to ask how many empty study drug kits will be returned at the next visit; and to remind them to note the time when they take their usual morning medications.

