- Telephone calls should be made to the patients in the observational cohort 2 weeks (\pm 3 days) prior to OV2 to monitor for AEs and to confirm the next study visit, and prior

to OV3, OV4, OV5, and OV6 to monitor for AEs, to confirm that the DLco assessment has been done/scheduled, and to confirm the next study visit.

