Upon completion of the 60-minute observations, resumption of normal medications is permitted for the remainder of the day (the patient may use the inhaled study drug 4 more times at home after he/she leaves the clinic on that day if needed for OFF episodes). The next visit will be scheduled. Clinic staff will arrange to speak with patients by telephone 1 to 3 days after TV/OV1 to monitor for AEs and to address any potential concerns or challenges with the inhaler systems or Inhaled Dosing Log. Additionally, clinic staff will arrange to speak with patients by telephone 2 weeks (\pm 3 days) before each visit for TV2, TV3, TV4, TV5, and TV6 to address any concerns or challenges with the inhaler systems, PD Diary, or Inhaled Dosing Log, to monitor for any AEs, to confirm the DLco assessment has been done/scheduled (prior to TV3, TV4, TV5, and TV6), to confirm the next study visit, to ask the patients how many empty study drug kits will be returned at the next visit, and also to remind patients of the study procedures

required prior to the next scheduled study visit (including completion of the PD Diary and Inhaled Dosing Log).

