APPENDIX 5: TIME AND EVENTS TABLE—OBSERVATIONAL VISIT 1 (OV1) (AT LEAST 7 DAYS AFTER SV2)

Procedures	Assess in Either ON or OFF State Unless Otherwise Noted	End of OV1	Post- OV1 Telephone Contact
Collect, review, sign, and date Screening ON/OFF Episodes Log and PD Diary	X		
Confirm DLco assessment ¹ has been performed prior to visit; and if not complete, re-schedule study visit	X		X
Record any changes in usual PD medication dose/regimen	X		
Concomitant medications	X		
PDQ-39 (in ON state)	X (ON)		
UPDRS Part 2 (preferably in ON state)	X (ON)		
S&E ADL (preferably in ON state)	X (ON)		
Physical examination (brief)	X		
Standard and orthostatic BP and HR	X		
Respiratory rate	X		
Electrocardiogram	X		
Spirometry (preferably in ON state)	X (ON)		
Clinical laboratory tests (including serum pregnancy test, if applicable)	X ²		
C-SSRS	X		
Epworth sleepiness scale	X		
QUIP	X		
Monitor for AEs	X		
Schedule next visit		X	
Post-OV1 telephone contact: call patient 2 weeks (± 3 days) before OV2			X

¹DLco is to be performed in a dedicated pulmonary facility and includes slow vital capacity maneuver, DLco, and spirometry. Preferably in the ON state.

²Document whether patient is fasting (≥4 hours after last snack or meal).

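### Only the CVT-301 arm has a scheduled adverse-event call at day 1 to 3 after baseline, and Section 10.3.1 omits that call's adverse-event purpose

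*Protocol*

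**What the plan says.** **CVT-301 arm.** In the synopsis text for TV/OV1, the block headed "In addition for the CVT-301 treated group only" ends with the early call: "Clinic staff will arrange to speak with patients by telephone 1 to 3 days after the visit to monitor for AEs". The call is also to cover inhaler and dosing-log problems. Section 10.3.2.1, on Treatment Visit 1, repeats it: "Clinic staff will arrange to speak with patients by telephone 1 to 3 days after TV/OV1 to monitor for AEs". Appendix 4 has a row for the call but gives no purpose.

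**The same call in Section 10.3.1.** Here the text reads: "Telephone calls should be made to patients in the CVT-301 treatment arm 1 to 3 days after TV1 to address any potential concerns or challenges", and the problems meant are those with the inhaler or the dosing log. AEs are not mentioned. The next bullet, on the later calls to the same patients, does list AE monitoring.

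**Observational cohort.** Section 10.3.2.2 includes AE monitoring at OV1, then ends with scheduling and discharge. The control bullet in Section 10.3.1 begins "Telephone calls should be made to the patients in the observational cohort 2 weeks" and places the first call before OV2, with AE monitoring among its purposes. Appendix 5 has one telephone row: "Post-OV1 telephone contact: call patient 2 weeks (± 3 days) before OV2".

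**Use of the data.** Section 12.5 tabulates AEs by treatment group and counts control AEs from OV1 onward as treatment-emergent. The synopsis and Section 12.5 add that "the time of onset of the TEAEs will be summarized". Section 9.2.1 states that patients and staff are not blinded.

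**The concern.** The by-group AE tables and the time-of-onset summary cover a period that starts at the first visit in both arms. In about the first two weeks of that period the arms are asked about AEs on different schedules. The extra enquiry falls just after the first doses of CVT-301, when early onset is most readily read as a drug effect. A short, mild event in the first days is asked about almost at once in a CVT-301 patient. In a control who does not volunteer it, the event is first asked about some days later, when it may be forgotten or misdated. Neither patients nor staff are blinded, so a common enquiry schedule is one of the few protections available for this comparison. The protocol states no caveat about the difference.

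The purpose of the call is a second problem. With about 100 planned sites, staff working from Section 10.3.1 are given no instruction to ask about AEs at that call, while staff working from the synopsis or Section 10.3.2.1 are.

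**Working it through.** The protocol gives no figure to reproduce. The check is date arithmetic and a count of scheduled contacts.

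**Inputs**
- Early CVT-301 call: day 1 to 3 after TV1 (synopsis; Sections 10.3.1 and 10.3.2.1; Appendix 4).
- OV2: 4 weeks ± 5 days after OV1, so day 23 to day 33 (Section 10.3.4; Appendix 7).
- Control call before OV2: 2 weeks ± 3 days ahead, so 11 to 17 days before OV2 (Section 10.3.1; Appendix 5).
- Calls before visits 2 to 6 with AE monitoring: 5 in each arm (Section 10.3.1).
- Visits 2 to 6 with AE monitoring: 5 in each arm (Section 10.3).

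**First scheduled AE contact after visit 1**
- CVT-301: day 1 to 3.
- Control, nominal: 28 − 14 = day 14.
- Control, earliest: (28 − 5) − (14 + 3) = 23 − 17 = day 6.
- Control, latest: (28 + 5) − (14 − 3) = 33 − 11 = day 22.

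**Scheduled AE contacts after visit 1**

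| Period | CVT-301 | Control |
|---|---|---|
| Through visit 2 | 1 early call + 1 pre-visit call + 1 visit = 3 | 1 pre-visit call + 1 visit = 2 |
| Through visit 6 | 1 + 5 calls + 5 visits = 11 | 5 calls + 5 visits = 10 |

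If the early call were made in both arms, the counts would be 3 and 3 through visit 2, and 11 and 11 through visit 6.

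**Could the early call be read as applying to controls?** Section 10.3.2.1 times it from TV/OV1, a label that covers both arms. The sentence stands in the section for the CVT-301 group, however. The bullet in Section 10.3.1 names that arm: "Telephone calls should be made to patients in the CVT-301 treatment arm 1 to 3 days after TV1". In the synopsis the block for all patients begins only after the call. Section 10.3.2.2 and Appendix 5 contain no early call, so the asymmetry is consistent across the document.

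**Purpose of the call.** The synopsis and Section 10.3.2.1 include AE monitoring, Section 10.3.1 gives only device and log problems, and Appendix 4 is silent. The first two cannot be reconciled with the third by reading Appendix 4.

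**The case against.** The strongest reply is that this is a deliberate and openly stated safety measure. CVT-301 patients have just had a first supervised dose and are starting to dose themselves at home, whereas controls start nothing at OV1. Section 10.3 says that procedures will differ between the groups. That is a good reason to keep the call. It is no reason against asking controls the same question, and it does not explain why Section 10.3.1 leaves AEs out.

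Other parts of the reply also limit the point.

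- **Later capture.** A reader might infer that early control events are missed. The document does not support this. Section 11.1.8 lets AEs be volunteered and has both arms asked at each visit about problems since the last one. The two-week call is a further opportunity. The difference is in promptness and recall.
- **Objectives.** The between-group objective in Section 6 concerns pulmonary safety. AE reports serve to characterise CVT-301, and the planned AE and onset summaries are descriptive. No conclusion on spirometry depends on this call.
- **Other contacts.** The remaining scheduled contacts match in number only. CVT-301 patients are dosed under supervision at every treatment visit and observed for 60 minutes afterwards. From TV2 they also wait in clinic until OFF and are watched for dyskinesia. A control call would not make ascertainment equal overall.
- **Section 10.3.1.** Omitting the AE purpose does not forbid recording AEs. Section 11.1.8 requires all AEs to be recorded, so it does not follow that sites using Section 10.3.1 would collect none at this call. The gap is that they are not told to ask.

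**Conclusion.** The point holds as a minor matter of design and wording. One scheduled AE enquiry, at day 1 to 3, is made in the CVT-301 arm only. Controls are next asked at nominal day 14, with a range of day 6 to day 22 if the visit and call windows are both used in full. The protocol also contradicts itself on whether that call includes AE enquiry.

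The consequence is confined to prompt solicitation of short, mild early events and their onset dates in descriptive by-group summaries. A reader might go further and attach a percentage to the excess of early AEs in the CVT-301 arm. The protocol gives neither an early event rate nor a recall rate, so any such figure would rest on invented inputs, and none is offered. Nor would a matching call allow an early excess to be read purely as drug effect: the study stays open-label, and the longer in-clinic observation of CVT-301 patients remains.

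**What to change.** 1. In Section 10.3.1, add AE monitoring to the purposes of the day 1 to 3 call so that it agrees with the synopsis and Section 10.3.2.1.
2. Add the same AE call, with the same question, for controls 1 to 3 days after OV1. This changes Section 10.3.1, Section 10.3.2.2, Appendix 5 and the synopsis.

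The cost is a wording change and about 115 short calls by existing site staff, one for each planned control in Section 12.1.

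AE tables that leave out events first reported at the early call would not be an adequate substitute. They would remove events from the CVT-301 arm only, including first-dose events that a safety study most needs, although many of these would also have been reported at the two-week call.

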4. LIST OF ABBREVIATIONS

ADL	Activities of Daily Living
AE	adverse event
ANCOVA	analysis of covariance
ATS	American Thoracic Society
AUC	area under the plasma concentration-time curve
AUC _{last}	area under the plasma concentration-time curve from time zero to the time of the last quantifiable concentration
BP	blood pressure
CD	carbidopa
CD/LD	carbidopa/levodopa
CFR	Code of Federal Regulations
C _{max}	maximal plasma concentration
COMT	catechol-O-methyltransferase
COPD	chronic obstructive pulmonary disease
CRO	contract research organization
C-SSRS	Columbia-Suicide Severity Rating Scale
DDI	dopamine decarboxylase inhibitor
DPPC	dipalmitoyl phosphatidylcholine
DBP	diastolic blood pressure
DBS	deep brain stimulation
DLco	carbon monoxide diffusing capacity
DSMC	Data Safety Monitoring Committee
ECG	electrocardiogram
eCRF	electronic case report form
ERS	European Respiratory Society
FEV1	forced expiratory volume in 1 second
FPD	fine particle dose (i.e., pulmonary-delivered dose)
FDA	Food and Drug Administration
FVC	forced vital capacity
GCP	good clinical practice
GI	gastrointestinal
hCG	human chorionic gonadotropin
HIPAA	Health Insurance Portability and Accountability Act of 1996

HPMC	hydroxypropyl methylcellulose
HR	heart rate
ICH	International Conference on Harmonisation
IEC	Independent Ethics Committee
IFU	Instructions for Use
IND	Investigational New Drug
IRB	Institutional Review Board
LD	levodopa
LIP	levodopa inhalation powder (CVT-301)
MAO-B	monoamine oxidase-B
MedDRA	Medical Dictionary for Regulatory Activities
mmHg	millimeters mercury
MMRM	Mixed Model for Repeated Measurements
MMSE	Mini Mental State Examination
NaCl	sodium chloride
NHANES III	Third National Health and Nutrition Examination Survey
NOAEL	no-observed-adverse-effect level
PD	Parkinson's disease
PDQ-39	39-Item Parkinson's Disease Questionnaire
PGI-C	Patient Global Impression of Change
PK	pharmacokinetic
PRN	as needed
QUIP	Parkinson's Disease Impulsive-Compulsive Disorders Questionnaire
RR	respiratory rate
S&E	Schwab and England
SAE	serious adverse event
SAP	statistical analysis plan
SBP	systolic blood pressure
SOP	standard operating procedure
SUSAR	suspected unexpected serious adverse reaction
SV1	Screening Visit 1
SV2	Screening Visit 2
T0	time of completion of inhalation of the last capsule of inhaled study treatment administered
t _{max}	time to maximal drug concentration
TEAE	treatment-emergent adverse event

TV/OV1	Treatment Visit/Observational Visit 1
TV/OV2	Treatment Visit/Observational Visit 2
TV/OV3	Treatment Visit/Observational Visit 3
TV/OV4	Treatment Visit/Observational Visit 4
TV/OV5	Treatment Visit/Observational Visit 5
TV/OV6	Treatment Visit/Observational Visit 6
UK	United Kingdom
UPDRS	Unified Parkinson's Disease Rating Scale
USA	United States of America

